## 1.2 Study Design Configuration

This is an open-label, proof-of-concept, single group study in newly diagnosed adult patients and adult patients resistant to corticosteroid tapering with moderate to extensive BP.

The study will consist of three periods:

- A screening period of up to 4 weeks
- An open-label treatment period lasting 4 weeks consisting of IV infusion of bertilimumab at Visit 2 (Day 0), Visit 3 (Day 14) and Visit 4 (Day 28)
- A safety and efficacy follow-up period of approximately 56 days plus a follow-up phone call 2 and 4 months following Visit 8 (Day 84)

### 2 Centers

This is a multicenter trial. Up to 10 sites in Israel and US will participate in this study.

# 3 Study Objectives

## 3.1 Primary Objective

To evaluate the safety of bertilimumab in newly diagnosed patients and patients resistant to corticosteroid tapering with moderate to extensive BP.

## 3.2 Secondary Objectives

To evaluate the preliminary evidence of clinical efficacy, pharmacokinetics (PK) and pharmacodynamic (PD) effect of bertilimumab in newly diagnosed patients and patients resistant to corticosteroid tapering with moderate to extensive BP.

## 3.3 Exploratory Objectives

To determine the change from Visit 2 (Day 0) to Visit 5 of Peripheral Blood Mononuclear Cell (PBMC) biomarkers.

## 4 Treatment Groups

This is a single arm trial, where all eligible patients will be treated with investigational product - Bertilimumab.

# 5 Study Schedule

**Table 1 Schedule of Study Events** 

Study Procedures	Screening Treatment Period				Follow-up Period a						Early Discontinuation b
Visit	1	2	3	4	5	6	7	8	9º	Phone call	-
Study Day (visit window +/- 2 day)	-28 to -1	0	14 (+/-2)	28 (+/-2)	42 (+/-2)	56 (+/-2)	70 (+/-2)	84 (+/-2)	118 (+/-2)	Approx. days 144 and 204	-
Informed consent	X										
Inclusion/exclusion criteria	X	X									
Demographic & medical history	X										
Karnofsky performance status	X										
Physical examination c	Xc	X*	X*	X*	X	X	X	X			X
Vital signs	X	$X^d$	$X^d$	$X^d$	X	X	X	X			X
ECG	X							X			X
Hematology (including eosinophil count) and biochemistry e	X f	X*	X*	X*	X			X			X
Serum eotaxin-1		X*	X*	X*	X	X	X	X			X
Screen for active/latent tuberculosis, g	X										
Skin punch biopsy for H&E and eosinophil count	X				X h						
Skin punch biopsy for DIF on salt split skin	X										
IIF and BP180 & BP230 auto antibodies	$\mathbf{X}^{\mathrm{j}}$	X*	X*	$X^*$	X	X	X	X			X
Assessment of BP severity	X										
Serology (HIV, HBV, HCV, CMV) e	X			•	•	•	•	•	•		
Urine β-hCG i		$X^*$	$X^*$	$X^*$	X			X			
Anti-bertilimumab antibodies		$X^*$	X*	$X^*$	X	X	X	X			X
PK (bertilimumab) blood sampling		$X^k$	X k	$X^k$	X	X	X	X			X
PBMC biomarker blood sampling		$X^*$			X						
Semen analysis		Xl	$X^{l}$	$X^{l}$					X		X m
Bertilimumab infusion		X	X	X							
BPDAI (including Pruritus evaluation) and lesion	X**	X*	X*	X*	X	X	X	X			X
healing assessment											
ABQOL questionnaire	X**	X*	X*	X*	X	X	X	X			X
Corticosteroid management	X	X	X	X	X	X	X	X	X	X	

Prior and concomitant medications	X	X*n	X*n	X*n	X	X	X	X	X	X	X
Adverse events	X	X*n	X*n	X*n	X	X	X	X	X	X	X
Infusion reaction assessment		Χ°	Χo	Χo							
Photography	X	X*	X*	X*	X	X	X	X			X

Note: Ability to taper steroids during scheduled or unscheduled visits will be determined by the investigator based on patient response.

- \* Denotes assessment will be done pre-dose
- \*\* To be performed if possible prior to commencement of corticosteroid regimen
- a Visits 3 through 9 have a ±2-day window. The window is calculated from the actual visit day compared to baseline (Day 0), (e.g., for Visit 6 (Day 56) the window would be Day 54 to Day 58).
- b At this visit, the activities to be performed will relate to the study period at which time the patient discontinued.
- c Physical examination including weight; height measurement at screening only.
- d Vital signs will be measured pre-dose (any time prior to the initiation of treatment infusion), immediately at the completion of treatment infusion (approximately 30 minutes after initiation) and approximately 2 hours following initiation of treatment infusion.
- e Clinical laboratory assessments will be performed by a local laboratory for the screening visit and a central laboratory for every subsequent visit.
- f Biochemistry will include serum  $\beta$ -hCG at screening for females of childbearing potential only.
- g The patient should be evaluated for active/latent TB as applicable (e.g., PPD, QFT, and/or chest x-ray)
- h The Visit 5 (Day 42) punch biopsies should be taken in the area of the previous biopsies, as much as possible.
- i Females of childbearing potential only.
- j IIF only at screening
- k Blood samples for bertilimumab (PK analysis) will be collected pre-dose and at the completion of treatment infusion (approximately 30 minutes after the initiation) and 2 or 4 hours following the initiation of treatment infusion. PK samples 30 minutes post-infusion should be taken as close to this time as possible.
- l Semen analysis will be performed for males pre-dose and close to the completion of infusion as possible. Pre-dosing samples can be taken up to 2 days prior to dosing. m Only for males with abnormal semen analysis results from Day 0, Day 14 or Day 28 compared to pre-dose at Visit 2 (Day 0). It should be noted that in practice semen samples were not collected.
- n Adverse events and concomitant medication information to be recorded pre-dose and 2 hours after the initiation of infusion.
- o Infusion reactions should be assessed at the completion of infusion (approximately 30 minutes after the initiation) and 2 hours following the initiation of treatment infusion

## 6 Analysis Populations

### **6.1 Safety Analysis Population**

The Safety analysis population will consist of all patients enrolled in the trial who received at least one infusion of bertilimumab 10 mg/kg.

Specifically, at least one CRF item "Date of Drug Administration" is completed.

## **6.2 Efficacy Analysis Populations**

### 6.2.1 PK Population

The PK population will include patients from whom PK samples were collected. Samples were collected at three timepoints: pre-dose, 30 minutes post-infusion and 2 or 4 hours post-infusion (depending on the protocol version executed) and at the follow-up visits. The following PK parameters will be calculated Cmax, Tmax, Cavg, Cmin, λz and t1/2. Additional PK parameters will be calculated if deemed necessary.

### **6.2.2 Efficacy Population**

The Efficacy population will be a subset of the Safety population. All patients in the Efficacy population will have the visit score on the Bullous Pemphigoid Disease Area Index (BPDAI) at baseline and at least one post baseline BPDAI score.

"Baseline" is defined as the last measurement obtained before the treatment initiation.

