2.2 STUDY ENDPOINTS AND OUTCOMES

Primary Endpoints

Safety Endpoints

Safety will be evaluated on the basis of the following parameters:

- Adverse events (AE)
- Infusion reactions
- Injection site reactions
- Physical examination
- Vital signs (blood pressure, heart rate, temperature)
- ECG
- Concomitant medications
- Laboratory evaluation (hematology, biochemistry, anti-bertilimumab antibodies)

Secondary Endpoints

Efficacy Endpoints

- Proportion of patients who achieve a reduction in the Total Activity Score of the BPDAI score of at least 50%, 75% and 90% at visits 5 (Day 42), 6 (Day 56), 7 (Day 70), or 8 (Day 84) compared to:
 - Screening, if patient is resistant to corticosteroid tapering
 - Visit 2 (Day 0), if patient is newly diagnosed.
- Proportion of patients who have tapered to prednisone dose of ≤10 mg/day at Visit 8 (Day 84) and/or 2 and 4 months after Visit 8 (Day 84)
- Proportion of patients who achieve control of disease activity at Visits 5 (Day 42), 6 (Day 56), 7 (Day 70), or 8 (Day 84)
 - Ocurrol of disease activity is defined as the time when at least two of the following occur: new lesions cease to form, established lesions begin to heal and/or pruritic symptoms start to abate. Control of disease activity will be assessed by the BPDAI and the investigator's assessment of lesion healing.
- Mean time to control of disease activity from:
 - Screening, if patient is resistant to corticosteroid tapering
 - Visit 2 (Day 0), if patient is newly diagnosed
- Change in BPDAI score at each scheduled measurement timepoint compared to:
 - Screening, if patient is resistant to corticosteroid tapering
 - Visit 2 (Day 0), if patient is newly diagnosed
- Change in BPDAI pruritis component (Visual Analogue Scale) at each scheduled measurement timepoint compared to:

- Screening, if patient is resistant to corticosteroid tapering
- Visit 2 (Day 0), if patient is newly diagnosed
- Change in ABQOL score at each scheduled measurement timepoint compared to:
 - Screening, if patient is resistant to corticosteroid tapering
 - Visit 2 (Day 0), if patient is newly diagnosed

Pharmacokinetic (PK) Endpoints

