### Total BPDAI Score

**Total BPDAI** score is defined as sum of the Total Activity scores and BPDAI Damage / Pigmentation Score. Higher scores indicate greater disease activity.

• Change in **Total Activity Score** of BPDAI from Baseline to all subsequent visits

Change in Total Activity Score =

(Baseline Total Activity BPDAI - Visit *t* Total Activity BPDAI)

• Change in Total BPDAI Score from Baseline to all subsequent visits

Change in Total BPDAI Score = (Baseline Total BPDAI - Visit t Total BPDAI)

Note: larger positive difference indicates greater improvement.

 Percent change in Total Activity Score of BPDAI from Baseline to all subsequent visits

Percent Change in Total Score = 100\*(Baseline Total Activity BPDAI – Visit t Total Activity BPDAI) / Baseline Total Activity BPDAI

Percent change in Total BPDAI Score from Baseline to all subsequent visits
 Percent Change in Total BPDAI Score = 100\*(Baseline Total BPDAI – Visit t Total BPDAI) / Baseline Total BPDAI

Note: larger positive difference indicates greater improvement.

In addition, percent change in Total Activity score of BDPAI will be further divided into 4 categories:

- 1. # subjects with >= 90% reduction in BPDAI total activity score
- 2. # subjects with >=75% reduction in BPDAI total activity score
- 3. # subjects with >=70% reduction in BPDAI total activity score
- 4. # subjects with >= 50% reduction in BPDAI total activity score

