### 7.2.2 Additional Efficacy Endpoints

### **BPDAI Pruritus Component (VAS) Score**

The following three VAS sub-scores will be defined:

- VAS Sub-Score I: How severe has your itching been over the last 24 hours
- VAS Sub-Score II: How severe has your itching been over the past week
- VAS Sub-Score III: How severe has your itching been over the past month

The Total Pruritus VAS score is defined as the sum over the three sub-scores. If at least one of the sub-scores is missing, the total is not defined.

• Change in BPDAI Pruritus Component (VAS) (sub-scores and total) from baseline to all subsequent visits

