### **Quality of Life**

- The autoimmune bullous diseases quality of life (ABQOL) questionnaire total score (auto-calculated in the CRF), by visit
- Change in ABQOL total score from baseline to all subsequent visits.

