## 7.4 PD Endpoints

Following are the study PD endpoints.

If more than one value is obtained per-patient, per-test or per-time point, the average will be calculated.

- Eosinophil Absolute Count (serum), by visit; and change in Eosinophil Absolute
   Count compared to Baseline
- Hematoxylin and Eosin (from biopsy tissue); and change in Hematoxylin and Eosin compared to Screening
- Eotaxin-1 (serum concentration); and change in serum Eotaxin-1 level at each scheduled timepoint compared to Baseline
- BP 180 autoantibody (serum concentration); and change in BP 180 autoantibody compared to Baseline
- BP 230 autoantibody (serum concentration); and change in BP 230 autoantibody compared to Baseline
- Eosinophil Cationic Protein (ECP) (serum concentration); and change in ECP compared to Baseline

IgE (serum concentration); and change in IgE compared to Baseline
 It should be noted that ECP and IgE data were collected from samples already available and the decision to test for these markers was made after the study was completed, so the protocol was not updated to include them.

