#### Vital Signs

- Descriptive statistics of blood pressure (systolic / diastolic), pulse and temperature by visit and by time point
- For each treatment visit, visits 2, 3 and 4, descriptive statistics of change from pre-dose to 30 minutes, 2 and/or 4 hours post-dose will be provided
- For visits 5, 6, 7 and 8, descriptive statistics of change from baseline pre-dose (visit 2) to each subsequent visit measure will be provided.

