### **Anti-bertilimumab**

- Descriptive statistics of anti-bertilimumab antibodies by visit
- Change from Baseline pre-dosing (at Visit 2) to each subsequent visit

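### For taper-resistant patients the SAP measures four BPDAI, pruritus and ABQOL endpoints from the last pre-infusion value (normally Day 0), the protocol measures them from Screening, and the SAP does not declare the change

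*SAP*

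**What the plan says.** Protocol section 2.2, and the synopsis in the same terms, sets the reference by patient type. For newly diagnosed patients it is Visit 2 (Day 0). For the others it is "Screening, if patient is resistant to corticosteroid tapering". This split is attached to the proportion with at least 50%, 75% or 90% reduction in BPDAI Total Activity, and to the changes in BPDAI, pruritus VAS and ABQOL. Mean time to control of disease activity carries it too.

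SAP section 6.2.2 has one rule for everyone: Baseline "is defined as the last measurement obtained before the treatment initiation". The endpoint definitions then use that term without a split:

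- **BPDAI (SAP 7.2.1):** change and percent change are computed from Baseline, and "percent change in Total Activity score of BDPAI will be further divided into 4 categories".
- **Pruritus (SAP 7.2.2):** "Change in BPDAI Pruritus Component (VAS) (sub-scores and total) from baseline to all subsequent visits".
- **Quality of life (SAP 7.2.2):** "Change in ABQOL total score from baseline to all subsequent visits".

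The analysis text in SAP 9.4 adds no split by patient type.

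**The concern.** The protocol and the SAP define the same endpoints against different reference scores for one of the two enrolled cohorts, and the SAP does not say that it has changed anything. A reader of the results would assume that the responder proportion is the one in the protocol.

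The two references need not agree. Screening runs from Day -28 to Day -1, and the protocol synopsis has corticosteroids managed during it, so disease activity can move in either direction before the first infusion. A fall before Day 0 counts towards response under the protocol and not under the SAP. A rise before Day 0 makes response easier to reach under the SAP than under the protocol. The study is meant to inform the decision on further development, and the SAP places BPDAI among its main efficacy endpoints, so the reference behind the responder rate should be visible.

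**Working it through.** **Is the SAP's Baseline really Day 0?** Protocol 5.4.1 and 5.4.3 and the schedule in Appendix A place BPDAI (with pruritus VAS) and ABQOL at Screening and again before dosing at Visit 2. The last pre-infusion value is therefore the Visit 2 score unless that score is missing. If it is missing, the Screening score takes its place and the two documents agree. They also agree for newly diagnosed patients.

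**Could Baseline be read as Screening for this cohort?** No. Where the SAP wants Screening it says so: SAP 7.4 has "change in Hematoxylin and Eosin compared to Screening", and SAP 9.3.2 takes physical examination shifts and ECG change from Screening. For vital signs, which are also measured at Screening, SAP 9.3.2 ties baseline to the pre-dose value at Visit 2.

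**Is the change declared anywhere?** The SAP does disclose other departures: semen samples not collected (footnote m to Table 1), incomplete data on control of disease activity (7.2.2), and ECP and IgE added after the study was completed (7.4). It has no such statement for the reference score.

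**What the change does to response.** The plan has no figure to reproduce here. Let S be the Screening score, D the Day 0 score and V a later score.

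- Protocol reduction: P = 1 − V/S
- SAP reduction: R = 1 − V/D, so V = D(1 − R)
- Hence P = 1 − (D/S)(1 − R), and P ≥ c exactly when R ≥ 1 − (1 − c)/(D/S)

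The documents give no BPDAI scores, so D/S is assumed over a range. The table shows the reduction from Day 0 that corresponds to meeting each protocol cut-off:

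| Assumed D/S | c = 50% | c = 75% | c = 90% |
|---|---|---|---|
| 0.75 | 33.3% | 66.7% | 86.7% |
| 0.90 | 44.4% | 72.2% | 88.9% |
| 1.00 | 50.0% | 75.0% | 90.0% |
| 1.10 | 54.5% | 77.3% | 90.9% |
| 1.25 | 60.0% | 80.0% | 92.0% |
| 1.50 | 66.7% | 83.3% | 93.3% |

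For example, at D/S = 0.75 and c = 50%: 1 − 0.50/0.75 = 33.3%. A patient whose reduction from Day 0 lies between the tabled value and c is classified differently by the two documents.

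Two assumed patients, judged at the 50% cut-off:

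- S = 40, D = 30, V = 18. Protocol: (40 − 18)/40 = 55.0%, a responder. SAP: (30 − 18)/30 = 40.0%, not a responder.
- S = 20, D = 30, V = 14. Protocol: (20 − 14)/20 = 30.0%, not a responder. SAP: (30 − 14)/30 = 53.3%, a responder.

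At the planned maximum of 15 patients, one flip moves the pooled proportion by 1/15 = 6.7 percentage points.

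**What it does to absolute change.** For BPDAI, pruritus VAS and ABQOL, (S − V) − (D − V) = S − D. Each taper-resistant patient's change differs between the two documents by S − D, the same amount at every visit.

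**The case against.** The best counter-argument is that little hangs on this. The primary objective is safety, there is one arm, every analysis is descriptive, and no test or success criterion uses the reference. Day 0 is arguably the better reference for change after the drug, and the protocol itself labels Visit 2 as baseline in its visit headings. SAP section 10 lists all CRF data, so with at most 15 patients a reader could rebuild the Screening-referenced results. The ratios above are assumed; if screening was short, D/S may be close to 1 and few patients or none would flip.

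Much of this stands, and it limits the severity. It does not remove the fault. Listings let someone reconstruct an endpoint, but no planned table reports it. The protocol's general use of baseline for Visit 2 does not override a reference that section 2.2 states endpoint by endpoint.

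Three narrower objections deserve an answer:

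- **A fifth endpoint, time to control, is also referenced to Screening.** True, but SAP 7.2.2 openly reduces control of disease activity to individual patient data because the information is incomplete, so it is not part of this undeclared change.
- **The antibody wording in SAP 9.3.2, "Change from Baseline pre-dosing (at Visit 2) to each subsequent visit", proves little.** True: that antibody is not sampled at Screening. The reading rests on SAP 6.2.2 and on the places where the SAP names Screening.
- **Scheduled scores may not have been collected, and before steroids they are asked for only if possible.** This stands as a caution. The tables should show how many patients have a Screening score.

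**Conclusion.** The concern holds. Followed exactly, the SAP leaves four protocol-defined secondary endpoints uncomputed for the taper-resistant cohort: BPDAI response, BPDAI change, pruritus VAS change and ABQOL change. It does not disclose this. The fault is the undeclared departure, not the choice of Day 0.

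The size in practice is unknown, because the documents give neither BPDAI scores nor the number of taper-resistant patients. What can be shown is that a flip is possible in either direction whenever the Screening and Day 0 scores differ. Over assumed ratios of 0.75 to 1.50, the protocol's 50% criterion corresponds to anything from 33.3% to 66.7% on the SAP's scale. The 6.7-point shift per flip assumes all 15 planned patients are in the denominator; with fewer it is larger. Because the endpoints are secondary and descriptive, this should be fixed but does not threaten the primary objective.

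**What to change.** - In SAP 6.2.2 and 7.2, state that the single baseline departs from protocol 2.2 for taper-resistant patients, give the reason, and define both references.
- Identify the cohort from inclusion criteria 3a and 3b.
- For taper-resistant patients, report BPDAI response and the changes in BPDAI, pruritus VAS and ABQOL from Screening, labelled as protocol-defined, next to the same results from the last pre-infusion value. Give the number of patients with a score at each reference, since the SAP does not impute.
- Optionally, show these tables by cohort as well as pooled. This is an addition, not part of the correction.

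The cost is SAP wording and one extra set of descriptive tables. No new assessments are needed: the scores are scheduled at both Screening and Visit 2, and the protocol's version history shows that the taper-resistant cohort and the Screening scores were both added in version 6.0.

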#### Handling of missing data:

Missing data will not be imputed, i.e. only observed data will be used.

## 7 Definition of Endpoints

## 7.1 Safety Endpoints

## 7.1.1 Main Safety Endpoints

- Treatment related (possibly and probably) AEs
- Serious AEs (SAEs)
- Infusion reactions

### 7.1.2 Additional Safety Endpoints

- Treatment emergent AEs (occurring at or after the treatment initiation)
- Physical examination
- Vital signs (blood pressure, heart rate, temperature)
- ECG
- Concomitant medications
- Laboratory evaluation:
  - Hematology
  - Biochemistry
  - Anti-bertilimumab antibodies

## 7.2 Efficacy Endpoints

### 7.2.1 Main Efficacy Endpoints

Following are the study main efficacy endpoints:

### **Bullous Pemphigoid Disease Area Index (BPDAI)**

The following three activity sub-scores will be defined:

#### **Activity Sub-Score I:** Total Activity Cutaneous Erosions/Blisters defined as:

Total Erosions/Blisters Activity Score (auto calculated in the CRF) + 0.3\* (The corresponding total number of erosions/blisters)

If a body region is scored 3 or higher, the number of lesions = 0.

In other words, only if a body region is scored 1 or 2 the number of lesions should be provided.

#### Activity Sub-Score II: Total Activity Cutaneous Urticaria/Erythema/Other defined as:

Total Urticaria/Erythema Activity Score (auto calculated in the CRF) + 0.3\* (The corresponding total number of urticarial/erythematous lesions)

If a body region is scored 3 or higher, the number of lesions = 0.

In other words, only if a body region is scored 1 or 2 the number of lesions should be provided.

### Activity Sub-Score III: Total Activity Mucosa Erosions/Blisters defined as:

Total Activity Score (auto calculated in the CRF)

There is no lesion count for Mucosa.

Note (a) the number of lesions reported for each of 12 areas could vary between 1 to 3. Thus, the maximal possible total number of lesions is 36; (b) lesion counts are ONLY reported for a score of 1 (Erosions/Blisters: "1-3 lesions, none>1cm;" Urticaria/Erythema: "1-3 lesions, none>6cm") or 2 (Erosions/Blisters: "1-3 lesions, at least one>1cm;" Urticaria/Erythema: "1-3 lesions, at least one>6cm").

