5.4 EFFICACY ASSESSMENTS

5.4.1 Bullous Pemphigoid Disease Area Index (BPDAI)

The BPDAI (See Appendix D) will be completed at all visits with the exception of Visit 9 (Day 118) as indicated in the Schedule of Events (Appendix A). At treatment administration Visits 2 (Day 0), 3 (Day 14), and 4 (Day 28), the BPDAI should be completed pre-dose (any time prior the initiation of treatment infusion). In screening, the BPDAI should be performed, if possible, prior to commencement of corticosteroid regimen.

The BPDAI Pruritus Component Visual Analogue Scale (VAS) will be completed by the patient or their legally authorized representative and all other sections for the BPDAI will be completed by the investigator. Patients and investigators will be asked to complete their respective sections on the corresponding worksheets, which will serve as source documentation for this measurement. The study source documents should reflect any issues that may have occurred during completion.

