Appendix D: Bullous Pemphigoid Disease Area Index [1]

BPDAI					
SKIN	ACTIVITY		ACTIVITY		DAMAGE
Anatomical location	Erosions/Blisters	Number of Lesions if <3	Urticaria/ Erythema / Other	Number of Lesions if <3	Pigmentation Other
	0 absent		0 absent		Absent 0, present 1
	1 1-3 lesions, none > 1 cm diameter		1 1-3 lesions, none >6 cm diamter		
	2 1-3 lesions, at least one > 1 cm diameter		2 1-3 lesions, at least one lesion > 6 cm diameter		
	3 >3 lesions, none > 2 cm diameter	-	3 >3 lesions, or at least one lesion > 10 cm diameter		
	5 >3 lesions, and at least one >2 cm		5 >3 lesions and at least one lesion > 25 cm diameter		
	10 >3 lesions, and at least one lesion >5 cm diameter or entire area		10 >3 lesions and at least one lesion > 50 cm diameter or entire area		
Head					
Neck	J				
Chest					
Left arm)				
Right arm	1 =		1		
Hands	1 = 1		Jr		
Abdomen			les -		
Genitals					
Back/Buttocks	i				
Left leg					
Right leg					
Feet	1 = 1				
Total skin	/120		/120		
MUCOSA	Erosions/Blisters				
	1 1 lesion				
	2 2-3 lesions				
	5 >3 lesions, or 2 lesions >2cm			_	
	CONTRACTOR OF STREET				
	10 entire area				
Eyes					
Nose					
Buccal mucosa					
Hard palate					
Soft palate					
Upper gingiva					
Lower gingiva					
I ongue					
Floor of Mouth	+				
Labial Mucosa	4 ===				
Posterior	S-				
Pharynx					
Anogenital		-		-	
Total Mucosa					

TOTAL ACTIVITY SCORE	TOTAL DAMAGE SCORE

BPDAI Pruritus Component- VAS

□ Baseline □ Beginning Consolidation

 $\ \square$ Consolidation phase $\ \square$ End of Consolidation

Tapering phase
 Partial remission on minimal therapy

Complete remission on minimal therapy
 Partial remission off therapy

□ Complete remission off therapy □ Flare

A. How severe has your itching been over the last 24 hours?

0 1 2 3 4 5 6 7 8 9 10 None

Score out of 10=

B. How severe has your itching been over the past week?

0 1 2 3 4 5 6 7 8 9 10 None Severe

Score out of 10=

B. How severe has your itching been over the past month

0 1 2 3 4 5 6 7 8 9 10 None Severe

Score out of 10=

Average INTENSITY SCORE FOR PAST MONTH = (A+B+C)=

OR.

For BP patients with impaired mental functioning:

No evide	nce of itch (no excoriations)	0
Mild itch	(isolated excoriations up to two body sites)	10
Moderate	eitch (excoriations on ≥ 3 body sites, impairment of daily activity)	20
Severe it	ch (generalized excoriations, sleep impairment)	30
	TOTAL	

TOTAL SCORE /30

@University of Pennsylvania 2011

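### As printed, the BPDAI form asks for a lesion count only below three, but SAP 7.2.1 needs counts of one to three, and no rule covers a blank at exactly three

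*SAP*

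**What the plan says.** SAP 7.2.1 builds the Total Activity Score from two skin sub-scores and one mucosal sub-score. Sub-Score I is "Total Erosions/Blisters Activity Score (auto calculated in the CRF) + 0.3" times the total number of erosions or blisters. Sub-Score II has the same structure for urticaria and erythema: "Total Urticaria/Erythema Activity Score (auto calculated in the CRF) + 0.3" times the lesion total. For both, the SAP says that "only if a body region is scored 1 or 2 the number of lesions should be provided", and it sets the count to 0 in regions scored 3 or higher. The note under Sub-Score III says that "the number of lesions reported for each of 12 areas could vary between 1 to 3" and concludes: "Thus, the maximal possible total number of lesions is 36". The mucosa has no count.

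Protocol Appendix D defines skin scores 1 and 2 as one to three lesions, separated by lesion size. Beside each of the two skin activity columns it prints a count column headed "Number of Lesions if <3". Protocol 5.4.1 has investigators complete the BPDAI on "corresponding worksheets, which will serve as source documentation for this measurement".

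On gaps in the data, SAP 6.2.2 says "Missing data will not be imputed, i.e. only observed data will be used". The only instruction in the BPDAI section to replace an unfilled item by zero concerns damage scores.

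**The concern.** A region with exactly three lesions normally scores 1 or 2, so the SAP formula needs its count. Taken literally, the form does not ask for it. A programmer who meets that blank has two obvious choices. One is to sum the counts that are present, so that the blank adds nothing. The other is to set the sub-score, and with it the Total Activity Score, to missing. The SAP chooses neither. By contrast, for the pruritus total in SAP 7.2.2 it does say what happens when a component is missing.

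The Total Activity Score feeds the change, the percent change and the counts of patients with reductions of at least 50%, 70%, 75% and 90% in SAP 7.2.1. It also feeds the first efficacy endpoint listed in Protocol 2.2. The gap matters most for patients who are improving, because their regions move down into the one-to-three range.

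**Working it through.** **Inputs.** Weight of 0.3 per lesion, counts for scores 1 and 2 only, 12 areas and count range 1 to 3 (SAP 7.2.1); count requested only below 3, and the score definitions (Protocol Appendix D).

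**The SAP's own maximum.** 12 areas × 3 = 36, which reproduces the stated figure. With the heading as printed, the maximum is 12 × 2 = 24.

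**Which regions are affected.** For erosions and blisters, score 3 starts above three lesions, so exactly three lesions always scores 1 or 2. For urticaria and erythema, a region with three lesions of which one exceeds 10 cm scores 3. Its count is 0 under the SAP anyway, so it is not affected.

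**Contribution of one region** = score + 0.3 × count:

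| Lesions | Score 1, SAP | Score 1, blank adds 0 | Score 2, SAP | Score 2, blank adds 0 |
|---|---|---|---|---|
| 1 | 1.3 | 1.3 | 2.3 | 2.3 |
| 2 | 1.6 | 1.6 | 2.6 | 2.6 |
| 3 | 1.9 | 1.0 | 2.9 | 2.0 |

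The shortfall is 3 × 0.3 = 0.9 points per affected region. The ceiling is 12 × 0.9 = 10.8 per skin sub-score, or 21.6 over both.

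**Percent change** = 100 × (baseline − visit) / baseline, so a positive value is improvement. Single-region examples:

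- Score 1, two lesions, worsening to three: (1.6 − 1.9)/1.6 = −18.75% under the SAP; (1.6 − 1.0)/1.6 = +37.5% if the blank adds 0.
- Score 2 with three lesions, to score 1 with one: (2.9 − 1.3)/2.9 = 55.2% under the SAP; (2.0 − 1.3)/2.0 = 35.0% if the blank adds 0. A 50% responder is lost.
- Score 2 with two lesions, to score 1 with three: (2.6 − 1.9)/2.6 = 26.9% under the SAP; (2.6 − 1.0)/2.6 = 61.5% if the blank adds 0. A 50% responder is created.

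**If the blank is treated as missing.** No ordering is reversed, but the Total Activity Score is lost for that visit. If the visit is baseline, every change and percent change for that patient is lost.

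**Rough size across patients.** The documents give no lesion distribution, so this part is assumption. A simulation used one skin component, 12 regions and gamma-Poisson counts with a mean of 1.5 to 4 per region. It assumed a large lesion in 30% of regions with one to three lesions, a chosen score for regions with more than three lesions, and every three-lesion count blank and added as 0. Between 77% and 92% of patients then had at least one three-lesion region at baseline or follow-up. With a 60% fall in lesion counts, 5.8% to 7.3% of patients were misclassified at the 50% threshold. Of 15 patients that is 15 × 0.058 = 0.9 to 15 × 0.073 = 1.1, or about one. At 70%, 75% and 90% at most 3% were misclassified.

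**The case against.** The strongest objection is that everything rests on one character. The text was extracted from PDF, and the bar of ≤ is lost elsewhere: the study design part of the Protocol synopsis shows <40.0 mg/day for permitted prior corticosteroids where its inclusion criteria and Section 3.0 show ≤40.0. The extracted Appendix D table is visibly damaged. If the form reads ≤3, it agrees with the SAP and the mismatch disappears. Against this, <3 appears in both columns and a ≥ survives in the pruritus part of the same appendix. The doubt stands and can be settled only from the form itself.

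Second, the CRF is not in the documents. Protocol 5.4.1 does not say that the worksheets reproduce the Appendix D heading. The version history says the appendix was corrected in version 8.0, and the SAP acknowledges that more than one protocol version was in use. SAP 7.4 indicates that the SAP was finalised after the study was completed, and its note describes reported counts running from 1 to 3. That is evidence, though not proof, that 3 was captured.

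Third, Protocol 10.4 already sends missing data back to site staff. That provides a route for queries, but it does not tell the programmer what to do with a blank that remains.

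Fourth, the consequences are limited. The simulated errors partly cancel: the net shift in the 50% responder proportion was −1.3 to +3.6 points. Mean absolute error in percent change was 3.9 to 7.4 points with one skin component and 2.5 to 4.9 with two. The endpoint is secondary and descriptive; the primary objective is safety.

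**Conclusion.** As printed, the form and the SAP do not fit together, and the SAP has no rule for the blank that results. Each affected region either loses 0.9 points (1.9 becomes 1.0, or 2.9 becomes 2.0) or costs the Total Activity Score for that visit. This rests on two conditions: that the heading really is <3, and that sites followed it.

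A reader might infer that the BPDAI ordering in this trial is reversed, with three lesions scoring below two. The documents do not support that as a fact. It requires a blank to count as 0, and the SAP gives that treatment only to regions scored 3 or higher and to unfilled damage scores. A reader might also take the simulated percentages as estimates for this trial. They are not, because the lesion distribution and universal blanks are both assumed. How many patients are affected cannot be known from the documents. With up to 15 patients, about one responder is a plausible size under those assumptions.

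**What to change.** Check the form in the source PDF, the worksheets used under each protocol version, and the CRF. If counts of 3 were requested and recorded, the remaining gap is only the missing rule for blanks.

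Before the BPDAI analysis, query every blank count in a skin region scored 1 or 2. Then add to SAP 7.2.1, under Sub-Scores I and II:

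*If a region is scored 1 or 2 and the form used asked for the count only if <3, a blank count that the site confirms was not an omission is set to 3; this is a deduction from the form, not imputation under 6.2.2. A blank that cannot be resolved is not treated as 0, and results are shown with the count set to 3 and with the score missing.*

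The deduction is sound because scores 1 and 2 imply one to three lesions and such a form would have recorded one or two. The site's confirmation guards against turning a true omission into the maximum count.

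The cost is a short SAP addition, queries that Protocol 10.4 already provides for, and a second presentation of results if any blank stays unresolved. Because the SAP describes the study as completed, the form heading needs correcting only if the error is confirmed and the form will be used again.
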